21.9 Appendix 9: Country-Specific Requirements

AUSTRIA:

In compliance with the Austrian Drug Law Amendment Act of 2004, the following regulatory requirements will be applied to all study centers in Austria:

Pregnancy: §30. The clinical testing of drugs may only be carried out or continued in women of childbearing potential, with the exception of cases as stated in §44, if non-pregnancy is confirmed prior to and at adequate intervals during the clinical trial.

Clinical Trials in Emergency Situations:

§43a. (1) If a clinical trial, by its very nature, can only be conducted in emergency situations in which the consent of the legal representative cannot be obtained within a reasonable length of time, then a clinical trial may be conducted on a person who is not in a position to give his or her consent if:

1. there is no informative basis that the subject has objected to or would object to the clinical trial,
2. such research is implicitly required for the validation of data that were obtained from clinical trials on persons able to give their informed consent or by means of other research methods and which can only be conducted in emergency situations,
3. the drug to be tested is intended to identify, heal, mitigate or prevent diseases in an emergency situation,
4. the application of the drug to be tested is indicated according to the latest findings in medical science in order to identify, heal or to mitigate a disease in emergency patients or to protect them from further diseases and the benefit of being included in the clinical trial outweighs the risk for the trial participant,
5. the conduct of the trial and the protocol have been approved by an ethics committee that has knowledge of the area of the disease in question and of the emergency situation concerned and the patient population involved or that has been advised on the clinical and ethical questions in the area of the disease in question and on the emergency situation concerned and the patient population involved, specifically for the conduct of clinical trials in emergency situations on persons who are unable to give their consent personally, and

6. in case of doubt the patient's interests, at all times, stand above public interests and the interest of science.

(2) The general public is to be informed about this circumstance in an appropriate manner at the clinical trial centre where a clinical trial is conducted on persons who are not in a position to give their consent.

(3) Should the patient recover and be in a position to give consent, he or she is to be informed immediately that a clinical trial has been or will be conducted in an emergency situation. He or she is to be informed as defined in §§38 and 39. The continuation of the clinical trial is only then allowed if informed consent has been given.

ITALY:

21.10 Appendix 10: RECIST, version 1.1

MEASURABILITY OF TUMOR LESIONS AT BASELINE

Measurable lesion:

A non-nodal lesion that can be accurately measured in at least one dimension (longest dimension) of:

- ≥ 10 mm with magnetic resonance imaging (MRI) or computed tomography (CT) when the scan slice thickness is no greater than 5 mm. If the slice thickness is greater than 5 mm, the minimum size of a measurable lesion must be at least double the slice thickness (e.g., if the slice thickness is 10 mm, a measurable lesion must be ≥ 20 mm)
- ≥ 10 mm calliper/ruler measurement by clinical examination or medical photography
- ≥ 20 mm by chest x-ray

Additionally, lymph nodes can be considered pathologically enlarged and measurable if:

- ≥ 15 mm in the short axis when assessed by CT or MRI (slice thickness recommended to be no more than 5 mm). At baseline and follow-up, only the short axis will be measured

Non-measurable lesion:

All other lesions including lesions too small to be considered measurable (longest diameter < 10 mm or pathological lymph nodes with ≥ 10 mm and < 15 mm short axis) as well as truly non-measurable lesions, which include: leptomeningeal disease, ascites, pleural or pericardial effusions, inflammatory breast disease, lymphangitic involvement of the skin or lung, abdominal masses/abdominal organomegaly identified by physical exam that is not measurable by reproducible imaging techniques.

Measurable disease: The presence of at least one measurable lesion. Palpable lesions that are not measurable by radiologic or photographic evaluations may not be utilized as the only measurable lesion.

Non-Measurable only disease: The presence of only non-measurable lesions.

Specifications by methods of measurements:

- The same diagnostic method, including use of contrast when applicable, must be used throughout the study to evaluate a lesion.
- All measurements should be taken and recorded in millimeters (mm), using a ruler or calipers.
- Ultrasound is not a suitable modality of disease assessment. If new lesions are identified by ultrasound, confirmation by CT or MRI is required.
- Fluorodeoxyglucose-positron emission tomography (FDG-PET) is generally not suitable for ongoing assessments of disease. However, FDG-PET can be useful in confirming new sites of disease where a positive FDG-PET scans correlates with the new site of disease present on CT/MRI or when a baseline FDG-PET was previously negative for the site of the new lesion. FDG-PET may also be used in lieu of a standard bone scan providing coverage allows interrogation of all likely sites of bone disease and FDG-PET is performed at all assessments.
- If FDG-PET/CT is performed then the CT component can only be used for standard response assessments if performed to diagnostic quality, which includes the required anatomical coverage and prescribed use of contrast. The method of assessment should be noted as CT on the case report form.

Clinical Examination: Clinically detected lesions will only be considered measurable when they are superficial (e.g., skin nodules). In the case of skin lesions, documentation by color photography, including a ruler/calipers to measure the size of the lesion, is required.

CT and MRI: Contrast enhanced CT with 5 mm contiguous slices is recommended.

Minimum size of a measurable baseline lesion should be twice the slice thickness, with a minimum lesion size of 10 mm when the slice thickness is 5 mm. MRI is acceptable, but when used, the technical specification of the scanning sequences should be optimised for the evaluation of the type and site of disease and lesions must be measured in the same anatomic plane by use of the same imaging examinations. Whenever possible the same scanner should be used.

X-ray: Should not be used for target lesion measurements owing to poor lesion definition. Lesions on chest X-ray may be considered measurable if they are clearly defined and surrounded by aerated lung; however, chest CT is preferred over chest X-ray.

EVALUATION OF TARGET LESIONS

Definitions for assessment of response for target lesion(s) are as follows:

- **Complete Response (CR):** Disappearance of all target lesions. Any pathological lymph nodes must be <10 mm in the short axis.

- **Partial Response (PR):** At least a 30% decrease in the sum of the diameters of target lesions, taking as a reference, the baseline sum of the diameters (e.g. percent change from baseline).
- **Stable Disease (SD):** Neither sufficient shrinkage to qualify for PR nor sufficient increase to qualify for PD.
- **Progressive Disease (PD):** At least a 20% increase in the sum of the diameters of target lesions, taking as a reference, the smallest sum of diameters recorded since the treatment started (e.g. percent change from nadir, where nadir is defined as the smallest sum of diameters recorded since treatment start). In addition, the sum must have an absolute increase from nadir of 5 mm.
- **Not Applicable (NA):** Target lesions not present at baseline.
- **Not Evaluable (NE):** Unable to classify using one of the five preceding definitions.

NOTE:

- If lymph nodes are documented as target lesions the short axis is added into the sum of the diameters (e.g. sum of diameters is the sum of the longest diameters for non-nodal lesions and the short axis for nodal lesions). When lymph nodes decrease to non-pathological size (short axis <10 mm) they should still have a measurement reported in order not to overstate progression.
- If at a given assessment time point all target lesions identified at baseline are not assessed, sum of the diameters cannot be calculated for purposes of assessing CR, PR, or SD, or for use as the nadir for future assessments. However, the sum of the diameters of the assessed lesions and the percent change from nadir should be calculated to ensure that progression has not been documented. If an assessment of PD cannot be made, the response assessment should be NE.
- All lesions (nodal and non-nodal) should have their measurements recorded even when very small (e.g., 2 mm). If lesions are present but too small to measure, 5 mm should be recorded and should contribute to the sum of the diameters, unless it is likely that the lesion has disappeared in which case 0 mm should be reported.
- If a lesion disappears and reappears at a subsequent time point it should continue to be measured. The response at the time when the lesion reappears will depend upon the status of the other lesions. For example, if the disease had reached a CR status then PD would be documented at the time of reappearance. However, if the response status was PR or SD, the diameter of the reappearing lesion should be added to the remaining

diameters and response determined based on percent change from baseline and percent change from nadir.

EVALUATION OF NON-TARGET LESIONS

Definitions for assessment of response for non-target lesions are as follows:

- **Complete Response (CR):** The disappearance of all non-target lesions. All lymph nodes identified as a site of disease at baseline must be non-pathological (e.g., <10 mm short axis).
- **Non-CR/Non-PD:** The persistence of 1 or more non-target lesion(s) or lymph nodes identified as a site of disease at baseline ≥ 10 mm short axis.
- **Progressive Disease (PD):** Unequivocal progression of existing non-target lesions.
- **Not Applicable (NA):** Non-target lesions not present at baseline.
- **Not Evaluable (NE):** Unable to classify using one of the four preceding definitions.

NOTE:

- In the presence of measurable disease, progression on the basis of solely non-target disease requires substantial worsening such that even in the presence of SD or PR in target disease, the overall tumor burden has increased sufficiently to merit discontinuation of therapy.
- In the presence of non-measurable only disease consideration should be given to whether or not the increase in overall disease burden is comparable in magnitude to the increase that would be required to declare PD for measurable disease.
- Sites of non-target lesions, which are not assessed at a particular time point based on the assessment schedule, should be excluded from the response determination (e.g. non-target response does not have to be "NE").

Frequency of tumor re-evaluation

Target and non-target lesions will be re-evaluated every 8 weeks.

Confirmation of Response

- To be assigned a status of PR or CR, a confirmatory disease assessment should be performed no less than 4 weeks (28 days) after the criteria for response are first met.

OVERALL RESPONSE CRITERIA

The table presents the overall response at an individual time point for all possible combinations of tumor responses in target and non-target lesions with or without the appearance of new lesions for subjects with measurable disease at baseline.

Evaluation of Overall Response for Subjects with Measurable Disease at Baseline

Target Lesions	Non-Target Lesions	New Lesions	Overall Response
CR	CR or NA	No	CR
CR	Non-CR/Non-PD or NE	No	PR
PR	Non-PD or NA or NE	No	PR
SD	Non-PD or NA or NE	No	SD
NE	Non-PD or NA or NE	No	NE
PD	Any	Yes or No	PD
Any	PD	Yes or No	PD
Any	Any	Yes	PD

Abbreviations: CR = complete response; NA = not applicable; NE = not evaluable; PD = progressive disease; PR = partial response; SD = stable disease

NOTE:

- Subjects with a global deterioration of health status requiring discontinuation of treatment without objective evidence of PD at that time should be classified as having "symptomatic deterioration." Objective response status is determined by evaluations of disease burden. Every effort should be made to document the objective progression even after discontinuation of treatment.
- In some circumstances, it may be difficult to distinguish residual disease from normal tissue. When the evaluation of CR depends on this determination, it is recommended that the residual lesion be investigated (fine needle aspirate/biopsy) to confirm the CR.

Reference:

21.11 Appendix 11: Response Criteria for NSGCT/NGGCT with Elevated Tumor Markers (AFP and β -HCG) at Baseline

Serum tumor markers alpha-fetoprotein (AFP) and beta-human chorionic gonadotropin (β -HCG) will be measured as indicated in the Time and Events Table

- **Marker-Negative Complete Response (CR-)** is defined as meeting the Response Evaluation Criteria in Solid Tumors (RECIST), v1.1 criteria for CR plus normalization of previously elevated tumor markers for a minimum of 4 weeks.
- **Marker-Positive Complete Response (CR+)** is defined as meeting the RECIST, v1.1 criteria for CR plus a tumor marker decrease for at least 4 weeks, but without complete normalization of previously elevated tumor markers.
- **Marker-Negative Partial Remission (PR-)** is defined as meeting the RECIST, v1.1 criteria for partial response (PR) plus normalization of previously elevated tumor markers for a minimum of 4 weeks.
- **Marker-Positive Partial Remission (PR+)** is defined as meeting the RECIST, v1.1 criteria for PR plus a tumor marker decrease for at least 4 weeks, but without complete normalization of previously elevated tumor markers.
- **Progressive Disease (PD)** is defined as a significant elevation ($\geq 50\%$) in tumor markers after 4 weeks of therapy; treatment will be stopped despite of radiological response.

References:

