4 STUDY DESIGN

This is a Phase II, open-label, non-randomized, multi-center study of oral dabrafenib in combination with oral trametinib in subjects with rare cancers with the BRAF V600E mutation. The following histologies will be included in this study: ATC, BTC, GIST, WHO Grade 1 or 2 glioma, WHO Grade 3 or 4 (high-grade) glioma, NSGCT/NGGCT, ASI, HCL and MM (Cohorts 1 to 9, respectively). This study is designed to determine the ORR of dabrafenib in combination with trametinib in subjects with rare BRAF V600E mutated cancers. Further supporting secondary objectives include the evaluation of duration of response, PFS, OS, and safety of the combination treatment. For each cohort, up to 25 evaluable subjects will be enrolled in the primary analysis cohort as defined in Section 5.1. If a given cohort is stopped early for efficacy, a histology specific expansion cohort may be opened to allow for additional patient enrollment (see Section 5.2). Only subjects with

histologically or cytologically confirmed advanced disease with no available treatment options as determined by locally or regionally available standards of care and by the treating physician's discretion will be eligible for enrollment. Subjects may be enrolled based on local BRAF V600E mutation results and mutation status will be confirmed by a central reference laboratory.

Subjects will undergo screening assessments prior to the start of treatment to determine their eligibility for study enrollment. Baseline disease assessment must be completed prior to the first dose of study treatment. For female subjects, a pregnancy test must be performed within 7 days prior to first dose of study treatment. No study procedures, including submission of tumor tissue, will be performed unless written informed consent has been obtained. Screening evaluations will include demography, medical history, review of prior treatment, physical, dermatologic and ophthalmic examinations, vital signs, 12-lead ECG, ECHO, clinical laboratory assessments including urinalysis and histologic-specific assessments. Screening assessments may be repeated at the discretion of the investigator.

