Non-measurable disease is defined as either unidimensionally measurable lesions, masses with margins not clearly defined, or lesions with maximal perpendicular diameters less than 10 mm.

All measurable and non-measurable lesions must be assessed using the same techniques as at baseline.

Complete response (CR): Requires all of the following:

- complete disappearance of all enhancing measurable and non-measurable disease sustained for at least 4 weeks
- no new lesions
- stable or improved non-enhancing (T2/FLAIR [fluid attenuated inversion recovery]) lesions
- subjects must be off corticosteroids (or on physiologic replacement doses only)
- stable or improved clinically.

Note: Subjects with non-measurable disease only cannot have a CR; the best response possible is stable disease (SD).

Partial response (PR): Requires all of the following:

- $\geq 50\%$ decrease compared with baseline, in the sum of products of perpendicular diameters of all measurable enhancing lesions sustained for at least 4 weeks
- no progression of non-measurable disease; no new lesions
- stable or improved non-enhancing (T2/FLAIR) lesions on same or lower dose of corticosteroids compared with baseline scan

- corticosteroid dose at the time of the scan evaluation should be no greater than the dose at time of baseline scan
- stable or improved clinically.

Note: Subjects with non-measurable disease only cannot have a PR; the best response possible is SD.

Stable disease (SD): Requires all of the following:

- does not qualify for CR, PR, or progression
- stable non-enhancing (T2/FLAIR) lesions on same or lower dose of corticosteroids compared with baseline scan.

In the event that the corticosteroid dose was increased for new symptoms and signs without confirmation of disease progression (PD) on neuro-imaging, and subsequent follow-up imaging shows that this increase in corticosteroids was required because of PD, the last scan considered to show SD will be the scan obtained when the corticosteroid dose was equivalent to the baseline dose.

NOTE: Stable doses of corticosteroids include subjects not on corticosteroids.

Disease progression (PD): Disease progression (PD) is defined by any of the following:

- $\geq 25\%$ increase in sum of the products of perpendicular diameters of enhancing lesions compared with the smallest tumor measurement obtained either at baseline (if no decrease) or best response, on stable or increasing doses of corticosteroids

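### Appendix 10's RECIST nadir wording leaves out the baseline sum; followed literally, it rules out target-lesion PD at the first scan and typically dates PD one scan late

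*Protocol*

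**What the plan says.** Protocol Appendix 10 (evaluation of target lesions) sets two conditions for PD. The relative one is "At least a 20% increase in the sum of the diameters of target lesions", measured from the lowest sum since treatment began. The absolute one is that "the sum must have an absolute increase from nadir of 5 mm". The same bullet then defines the term: "nadir is defined as the smallest sum of diameters recorded since treatment start". Baseline is not mentioned in it. The PR rule, by contrast, is measured against the baseline sum. SD is the residual category: "Neither sufficient shrinkage to qualify for PR nor sufficient increase to qualify for PD".

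Protocol section 4 fixes when baseline happens: "Baseline disease assessment must be completed prior to the first dose of study treatment". On the interval, Appendix 10 says "Target and non-target lesions will be re-evaluated every 8 weeks"; the Time and Events Table (footnote 27) lengthens it to 12 weeks after week 48.

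The glioma appendices handle the same issue differently. Appendix 14 (Grade 3 and 4) measures enhancing-lesion growth "compared with the smallest tumor measurement obtained either at baseline (if no decrease) or best response", and Appendix 13 (Grade 1 and 2) also names the baseline scan.

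SAP 2.4.1 derives best confirmed response from the investigator's call at each time point and states no nadir rule. SAP 2.6 lists ATC, BTC and ASI as the RECIST cohorts analysed for PFS. GIST and NSGCT/NGGCT are not on that list.

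**The concern.** A scan taken before the first dose was not recorded since treatment start. At the first on-treatment scan, the only sum that meets the wording is that scan's own. A tumour that has grown since baseline then shows no growth from nadir, fails the PD test and drops into SD. At later scans the reference is the smallest on-treatment sum, which is already inflated if the tumour grew before the first scan.

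What is at stake is mainly the date of progression. SAP 2.6.2 counts only radiological PD or death as events in the RECIST cohorts, and clinical progression does not count. It also censors at the last adequate assessment when new anti-cancer therapy starts before documented PD. Under the literal rule, a subject who grew early and moved to other therapy would be censored instead of counted as an event. The split of best response between SD and PD is exposed in the same way, and a week-8 SD passes the SAP's 42-day minimum (56 ± 3 days is day 53 to 59).

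**Working it through.** The plan states no figure to reproduce, so the check applies the rule under two references.

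**Inputs from the documents.** PD needs an increase of at least 20% and at least 5 mm over the reference; scans are every 8 weeks; PR is measured from baseline. **Assumed.** The lesion sums below are illustrative.

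**Rule.** With S0 the baseline sum and Sk the sum at scan k, target PD occurs at the first k where Sk ≥ 1.2 × R and Sk − R ≥ 5 mm.
- Literal: R = min(S1, …, Sk).
- Baseline included: R = min(S0, …, Sk−1).

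At k = 1 the literal reference is S1 itself, so growth is (S1 − S1)/S1 = 0% whatever S0 was.

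| Sums in mm, baseline first | Literal | Baseline included |
|---|---|---|
| 50, 65, 80 | week 16 (80/65 = 1.23, +15) | week 8 (65/50 = 1.30, +15) |
| 50, 65, then flat | not reached | week 8 |
| 50, 100, 110, 115 | not reached (115/100 = 1.15) | week 8 (100/50 = 2.00) |
| 50, 55, 60, 66 | week 24 (66/55 = 1.20, +11) | week 16 (60/50 = 1.20, +10) |
| 50, 40, 50 | week 16 (50/40 = 1.25, +10) | week 16 |

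**Constant growth.** Starting from 100 mm and growing by a fraction g per scan, the baseline-inclusive rule needs (1+g)^k ≥ 1.2. The literal rule needs (1+g)^(k−1) ≥ 1.2, which is one scan later. For g = 5, 10, 20 and 30%, PD falls at weeks 32, 16, 8 and 8 with baseline included, and at weeks 40, 24, 16 and 16 literally. The last row of the table shows that a tumour that shrinks first is unaffected.

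**Planned PFS summaries.** SAP 2.6.2 reports the median, quartiles and Kaplan-Meier estimates at 6, 12 and 24 months. Six months is 6 × 30.4375 / 7 = 26.1 weeks. A shift from week 8 to week 16 crosses no landmark and can matter only to a quartile or median in that range. A shift from week 24 to week 32 crosses the 6-month landmark, and a plateau after early growth can cross any of them.

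**Response endpoints.** SD and PD are both non-response, and PR does not use the nadir. The exception is a course such as 50, 65, 34, 34: 34/50 = 0.68, a 32% fall from baseline seen at two scans 8 weeks apart. Literally that is a confirmed PR. With baseline included it is PD at week 8, after which SAP Table 2-2 allows no response. Apart from such cases, duration of response is unaffected, because a RECIST responder's target sum has already fallen below baseline and the two references then agree.

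**The case against.** The strongest reply is that this is loose drafting that nobody would follow. Appendix 10 is headed RECIST version 1.1 and cites that guideline. Its note on unassessed lesions speaks of a sum serving as nadir for later assessments, which suggests that a scan is never its own reference; at the first scan the only earlier sum is baseline. SAP Table 2-2 keeps PD as best response when it is the only evaluable assessment after treatment starts, and the SAP's censoring reasons treat a missing baseline as preventing assessment of progression. Lesion guidance also sits in the procedures manual and imaging guideline, which are not among these documents. PFS by independent review is already planned as a sensitivity analysis.

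Much of this stands. It makes it plausible that investigators used baseline, and it shows that the authors expected early PD to be possible. It does not repair the rule. No passage says that baseline fills the gap, and the RANO appendices show that the authors could say so. Treating the nadir as an earlier on-treatment sum leaves the first scan with no reference and still gives the late date afterwards: for 50, 55, 60 the week-16 comparison is 60/55 = 1.09, not 60/50 = 1.20.

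A reader might infer that first-scan growth can never be PD and is in fact coded SD. The documents do not support that. New lesions and unequivocal non-target progression give PD at any scan, no text instructs SD coding, and the SAP takes the investigator's call without computing a nadir.

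**Conclusion.** The wording of the PD reference is defective and should be corrected. Its literal application cannot yield target-lesion PD at the first scan, and typically delays PD by one scan (about 8 weeks during the first 48 weeks) when the sum never falls below baseline. The exposure is investigator PFS and the SD/PD split in ATC, BTC and ASI. Confirmed ORR is affected only by a response after early growth, which should be rare.

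This rests on reading treatment start as the first dose. The size of any effect is unknown: it depends on how many subjects progressed by target growth alone and on what investigators did, and the documents give neither. A reader might also infer a fixed bias, such as at least 8 weeks per affected subject or a set number of percentage points on the PFS curve. That does not follow. Death or another route to PD can end PFS sooner, new therapy can censor it, and a plateau can lengthen the delay. Nor does the point reach PFS in GIST or NSGCT/NGGCT, since none is planned there.

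**What to change.** In Appendix 10, define the PD reference as *the smallest target-lesion sum on study, counting the baseline sum*, in both places in the bullet.

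In the SAP, keep investigator-assessed PFS as the endpoint and add a programmed check for the RECIST cohorts:
- recompute target-lesion PD from the recorded sums with baseline included;
- list every subject whose PD date or best response would change;
- query those records;
- report a sensitivity PFS if any differ.

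The check should not replace the investigator's assessments.

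The cost is small: one definition, one program and possibly one extra output. SAP 2.4.2 already plans a listing of investigator lesion assessments for ATC, BTC, GIST and ASI. Enrollment ended in June 2018, and the Amendment 11 rationale counts only 2 ATC subjects and 1 BTC subject still on treatment, so rewording alone would change few future assessments. The check is the part that matters. An empty list closes the point.
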